4.2.2.2 Restrictions on diet and lifestyle

Restrictions prior to PFT visits:

- Medication washout restrictions should be adhered to as described in [Section 4.2.2.1](#).
- The patient must remain in the building where the pulmonary function testing is performed and must return to the laboratory at least ten minutes prior to the start of each test. An exception is the travel to and from the overnight accommodation, which of course is allowed.
- On pulmonary function test days (including the Screening Visit), patients must refrain from strenuous activity for at least 12 hours prior to pulmonary function testing and throughout the testing period. Patients should also avoid cold temperatures, environmental smoke, dust or areas with strong odors (e.g. perfumes).
- Coffee, tea, chocolate, cola and other caffeine-containing beverages and foods, and ice-cold beverages are not allowed at least 2 hours prior to and during the pulmonary function testing at clinic visits. Decaffeinated beverages are acceptable.
- Smoking should be discouraged for the 12 hours prior to pulmonary function testing and throughout the test day and will not be permitted in the 30-minute period prior to spirometry.

A patient visit may be re-scheduled twice due to lack of medication washout compliance.

4.2.2.3 Restriction regarding women of childbearing potential

Women of childbearing potential must use the contraception methods described in the patient information.

4.3 TREATMENT COMPLIANCE

Patients are requested to bring all remaining trial medication including empty package material with them when attending visits. Trial medication adherence should be reviewed by the investigator and reported in the eCRF.

Estimating compliance to trial medication

Respimat[®] Inhaler compliance: Knowing the time interval between clinic visits, it is possible to calculate the number of puffs that should have been administered by the patient. The Respimat[®] Inhaler contains 60 actuations (30 daily doses). The dose indicator shows approximately how much medication is left. The dose indicator scale is divided into 4 quarters. One quarter used accounts for 7 days of treatment (14 actuations). When the pointer enters the red area of the scale, there is approximately medication for 7 days (14 actuations left). Once the dose indicator has reached the end of the red scale (i.e. all 30 daily doses have been used) the Respimat[®] inhaler is empty.

Diskus[®] Inhaler compliance: There is a counter on top of the Diskus[®] which indicates how many doses are left. It counts down to 0.

The acceptable medication compliance should have an overall value in the range 80% to 120%. If the compliance is less than 80% the patient needs to be re-trained.

Randomised patients should not be discontinued for lack of medication compliance without prior discussion with the sponsor.

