- The Respimat[®] treatment box will contain 1 Respimat[®] inhaler plus one drug-filled cartridge and contains sufficient medication for 30 days of treatment. The Respimat[®] inhaler will lock after 60 actuations have been administered and will no longer actuate any medication.
- The Diskus[®] treatment box will contain one Diskus[®] inhaler. Each Diskus[®] contains sufficient medication for 30 days of treatment. The Diskus[®] inhaler will be contained inside a foil pouch which will be heat-sealed and labelled, before being placed into the treatment box.

Labelling

Individual treatment boxes will have a medication identification label and a tear-off label. Each tear-off label should be attached to the drug accountability form which will be part of the ISF. The investigator or designee should complete the following information:

- Date of cartridge insertion, patient number and visit number should be entered at time of cartridge insertion on the inhaler booklet label.
- Investigator's name should be entered at the time of dispensing on the label of the treatment box.

For details of packaging and the description of the label, refer to the ISF.

Medication Dispensing

The assignment of Respimat[®] and Diskus[®] treatment boxes dispensed at the beginning of each treatment visit (Visit 2 and Visit 3) will be handled by an IRT system.

At randomisation (Visit 2), the site staff will phone or use the web to access the IRT and obtain medication numbers for each of the 3 Respimat[®] treatment kits and 3 Diskus[®] treatment kits to be dispensed to the patient for daily use during the 6 weeks between visits. Two of the treatment kits will be used by the patient and the third is a reserve kit.

The Respimat[®] and Diskus[®] medication and reserve kits will have unique medication numbers. One Respimat[®] inhaler will be primed by the site staff (see [Section 4.1.4](#)) and used to dose the patient at that site visit, and will continue to be used at home until 30 days of

treatment has been reached. The Diskus[®] Inhaler does not have to be primed and will be used for 30 days of treatment.

The second Respimat[®] kit will be primed and used by the patient to cover the remaining weeks until the next visit. The third Respimat[®] kit and the third Diskus[®] kit are reserve medication. This is to allow the patient the flexibility of not having to return to the site immediately to replace a lost or malfunctioning Respimat[®] or Diskus[®].

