7.3 TREATMENT COMPLIANCE

Only descriptive statistics are planned for this section of the report. Summary statistics will be given for percent compliance along with the number (%) of patients with compliance in the categories <80% or >120%, 80% - 120%.

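### Protocol 4.3 converts each quarter of the Respimat scale to 14 actuations and 7 days, which totals 56 and 28 rather than the stated 60 and 30, so Respimat compliance reads somewhat low in both arms.

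*Protocol*

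**What the plan says.** Protocol 4.3 describes the Respimat in one paragraph:

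- Content: the inhaler "contains 60 actuations (30 daily doses").
- Scale: "The dose indicator scale is divided into 4 quarters".
- Conversion: "One quarter used accounts for 7 days of treatment (14 actuations").
- Red area: "there is approximately medication for 7 days (14 actuations left").
- End of scale: reaching the end of the red area is equated with having used all 30 daily doses.
- Precision: "The dose indicator shows approximately how much medication is left".

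Protocol 4.1.6 says that the "inhaler will lock after 60 actuations have been administered". Appendix 10.1 also gives 60 puffs per inhaler and about 14 left at the red area.

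Flow Chart note 17 takes medication use from the dose counters of the two devices. Protocol 4.3 explains how to obtain the number of puffs due, sets an acceptable overall compliance of 80% to 120%, and asks for re-training below 80%. SAP 7.3 summarises percent compliance descriptively, with the "number (%) of patients with compliance in the categories <80% or >120%, 80% - 120"%. Neither document gives a formula for turning an indicator position into actuations used, or says how the Respimat and Diskus figures form one overall value.

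**The concern.** The quarter conversion cannot be right for the device described around it: four quarters at 14 actuations fall 4 short of the stated content. The sentence matters because nothing else in the documents tells a site how to convert the position of a partly used Respimat into puffs taken. A conversion that counts too few puffs lowers recorded compliance. Some patients truly at or above 80% could then be recorded below it, sent for re-training, and placed in the wrong SAP 7.3 category. The Diskus has a counter that shows the doses left, so it needs no such conversion.

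**Working it through.** **Inputs.** Capacity 60 actuations or 30 daily doses, 4 quarters, 14 actuations or 7 days per quarter (Protocol 4.3); lock at 60 (4.1.6); 2 inhalations once daily (4.1.1); six weeks between treatment visits, taken as 42 days, with two inhalers for use and one in reserve (Flow Chart, 4.1.6); threshold 80% (4.3).

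**Stated capacity.** 30 doses × 2 = 60, so content and posology agree.

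**Quarter conversion.** 4 × 14 = 56, not 60; 4 × 7 = 28, not 30. Equal quarters that agree with the content hold 60/4 = 15 actuations and 30/4 = 7.5 days. If only the red quarter holds 14, the other three hold (60 − 14)/3 = 15.3 each, so 14 per quarter still fails.

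**Due over one interval.** 42 × 2 = 84 actuations.

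**Case A: an emptied inhaler is scored as 60 and only the second is read by quarters** (equal quarters).
- Fully adherent patient: 84 − 60 = 24 from the second inhaler, or 24/15 = 1.6 quarters, read as 1.6 × 14 = 22.4. Recorded compliance is (60 + 22.4)/84 = 98.1%, which is 1.9% low.
- Trigger: a reading of 80% is 0.80 × 84 = 67.2 actuations, of which 7.2 are on the second inhaler. True use there is 7.2 × 15/14 = 7.71, so true compliance is 67.71/84 = 80.6%.
- Between 67.2 and 67.71 there is no whole number of puffs. At 68 puffs the reading is (60 + 8 × 14/15)/84 = 80.3%. In this case nobody at or above 80% is recorded below it.

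**Case B: no inhaler is emptied and all use is read by quarters** (equal quarters).
- Ratio: 14/15 = 93.3%, which is 6.7% low.
- Trigger: 80%/0.933 = 85.7%.
- Example at 85% true compliance, changing inhaler after 30 calendar days: 0.85 × 60 = 51 actuations from the first and 0.85 × 24 = 20.4 from the second, 71.4 in all. This is read as 71.4 × 14/15 = 66.6, and 66.6/84 = 79.3%, so re-training is triggered.
- In whole doses, 34/42 = 81.0% and 35/42 = 83.3% are recorded below 80%; 36/42 = 85.7% reads exactly 80%.

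**Sensitivity to unequal quarters.** With 15.3 actuations in each of the first three quarters, case A becomes (60 + 24 × 14/15.33)/84 = 97.5% for a fully adherent patient, with the trigger at 80.8%. Case B also grows: use within those three quarters is read at 42/46 = 91.3%.

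**Coarse reading.** If only whole quarters are read on the second inhaler, a fully adherent patient in case A records (60 + 14)/84 = 88.1% or (60 + 28)/84 = 104.8%.

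**The case against.** The strongest reply is that the 6.7% and 85.7% figures need a formula the documents do not contain. A reader might infer that every actuation is converted at 14 per quarter. Protocol 4.3 does not prescribe that, and it credits an inhaler at the end of its scale with all 30 doses, as the lock at 60 in 4.1.6 also implies. A fully adherent patient takes 84 actuations in an interval and so must empty one inhaler, which gives case A. This stands: 6.7% cannot be stated as a general understatement. Case B remains possible for patients who miss doses. Protocol 4.1.6 keeps the first inhaler in use for 30 days of treatment, and 4.1.4.1 gives about 30 days per inhaler. If that means calendar days, which the wording leaves open, such a patient changes inhaler before emptying the first.

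A second reply is that the indicator is only approximate, and that coarse reading matters more than 14 against 15. As the whole-quarter figures show, that is true of size. It does not excuse the conversion: the approximate wording attaches to the indicator and the red area, while the quarter sentence is unqualified and errs in one direction.

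Third, 15 per quarter is not proven either. The red area is put at about 14, Appendix 10.1 says that the indicator counts every turn of the base, and the documents do not say how priming turns relate to the scale. This also stands, so 15 is conditional on equal quarters.

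Finally, a reader might infer that compliance with active drug is understated in the tiotropium+olodaterol arm only, because the Respimat is the dummy in the other arm. The documents do not support that as a bias. The design is double-dummy, both arms follow the same Respimat schedule under blinding, and no compliance figure restricted to the active device is defined.

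**Conclusion.** The contradiction is real and rests on figures within one paragraph: 56 and 28 against 60 and 30. Used for partly used inhalers, the conversion understates Respimat compliance in both arms alike. Over 42 days with equal quarters, the size runs from case A (about 1.9% low at full adherence, trigger at about 80.6%) to case B (6.7% low, trigger at 85.7%). Which applies depends on whether an inhaler is emptied and how it is then scored. In case A the trigger misclassifies nobody; in case B it catches patients with true compliance from 80% to just under 85.7%.

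The consequences are small. Falling below 80% leads to re-training, and discontinuation for poor compliance needs prior discussion with the sponsor. SAP 7.3 is descriptive. A reader might expect the error to alter the per-protocol set, but violation C3.2 in SAP Table 6.2: 1 rests on serious non-compliance in monitoring reports and a meeting decision, not on this percentage. No efficacy analysis is affected, and there is no between-arm bias in recorded compliance. This is a minor correction.

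**What to change.** In Protocol 4.3, align the quarter conversion with the stated content: about 15 actuations and 7.5 days if the quarters are equal, or the actual graduation of the scale if they are not. State that an emptied or locked inhaler counts as 60 actuations, and reconcile the approximate red-area figure with the quarter figure. Put the percent-compliance formula on that base in 4.3 and SAP 7.3, including how the Respimat and Diskus figures form the overall value. The 80% to 120% range itself is not in question.

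The cost is a few sentences and one derivation rule, with no new measurements. If the database holds only site-calculated percentages rather than indicator readings, which the documents do not settle, the choice is between recalculating from source records and adding a footnote to the compliance table.

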5. VARIABLES AND THEIR ASSESSMENT

5.1 TRIAL ENDPOINTS

5.1.1 Primary Endpoint(s)

The primary efficacy variable will be forced expiratory volume in one second (FEV₁), obtained during pulmonary function testing.

The primary endpoint is FEV₁ Area Under the Curve (AUC)_{0-24 h} response (change from baseline) [L] after 12 weeks of treatment.

FEV₁ AUC_{0-24 h} is calculated as the area under the FEV₁-time curve from 0-24 hours post-dose using the trapezoidal rule, divided by the duration (24 hours) and reported in Liters. FEV₁ AUC_{0-24 hr} response (change from baseline) is defined as FEV₁ AUC_{0-24 h} minus baseline FEV₁.

The same definition applies to FEV₁ AUC_{0-12h}.

The mean of the two pre-dose pulmonary function test measurements at Visit 2, 1 hour prior and 10 minutes prior to the administration of the first dose of the randomised treatment, is defined as the baseline FEV₁.

5.1.2 Secondary Endpoint(s)

- FEV₁ AUC_{0-12 h} response (change from baseline) [L] after 12 weeks treatment
- Trough FEV₁ response (change from baseline) [L] after 12 weeks treatment
- Peak 0-3h FEV₁ response (change from baseline) [L] after 12 weeks treatment
 - Trough FEV₁ is defined as the mean of the FEV₁ value measured at 23 hrs and at 24 hrs after trial medication administration. Trough FEV₁ response (change from baseline) is defined as trough FEV₁ minus baseline FEV₁.
 - Peak_{0-3h} is defined as the maximum value measured within the first three hours post dosing.

5.2 ASSESSMENT OF EFFICACY

5.2.1 Pulmonary function testing (PFT)

MasterScope[®] CT spirometers will be provided to sites for the on-site spirometry measurements. The spirometers and their use, including daily calibration on test days, must meet ATS/ERS criteria [[P05-12782](#)]. Spirometry will be conducted with the patient in a seated position having abstained from medications as specified in [Section 4.2.2.1](#), and it is preferable that the same trained individual performs the PFTs for a given patient. The best of three efforts will be defined as the highest FEV₁ and the highest FVC each obtained on any of three blows meeting the ATS criteria (with a maximum of five attempts). The highest FEV₁ and FVC will be selected regardless of whether they come from different spirometric maneuvers or from the same maneuver. The 24-hour clock time of the first maneuver for each PFT time point will be recorded.

The clock time of the start and end of inhalation procedure of trial medication will be captured by the MasterScope[®] CT spirometer.

At Visit 2, pulmonary function tests will be performed to determine patient eligibility and assess bronchial reversibility (for patient characterization). Further details of reversibility testing are described in [Appendix 10.5](#). At Visit 2 the study medication will be self-administered between 07:00 a.m. and 10:00 a.m. At Visits 3 and 4 the study medication is to be self-administered within ± 30 minutes of the time of administration at Visit 2 (please refer to [Section 4.1.4.1](#) for time window in inhalation of trial medication).

At Visits 3 and 4 the PFT will be measured up to 24 hours after dosing of trial medication (please see specified time points in the [Flow Chart](#)). Also refer to the Flow Chart for the time windows for the PFTs.

Refer to [Section 4.2.2.2](#) for restrictions regarding concomitant therapy prior to PFTs. Refer to [Section 4.2.2.2](#) for restrictions on diet and life style prior to PFTs. Refer to the Flow Chart for the timing of PFTs.

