| 5. | Women of child-bearing potential: Serum pregnancy test is to be completed at Visit 1. Urine pregnancy test (dipstick) is to be completed at Visits 2, 4, and 5. Pregnancy testing is to be completed prior to study drug administration. |
| 6. | If needed, the patient will be re-instructed/re-educated in the use of the RespiMat [®] and Diskus [®] devices but the patient should not inhale from the placebo inhaler at |

| | |
|-----|--|
| | these visits. |
| 7. | Site staff will telephone the patient 1 – 2 days prior to visits 2, 3 and 4 to remind the patient of medication restriction requirements and that they should not inhale trial medication at home on the morning of a clinic visit. |
| 8. | Collect dispensed rescue medication during the course of the trial (whenever applicable). |
| 9. | Including drug accountability check of dispensed ProAir [®] HFA rescue medication and Atrovent HFA (if applicable). |
| 10. | Visit 1: Reversibility testing using 400µg albuterol [Note: reversibility is not an inclusion criterion]. See Appendix 10.5 |
| 11. | Visit 2*: 
 • Two pre-dose PFTs: One at 1hour pre-dose and a second at 10 minutes prior to inhalation of dose of trial medication. • Post-dose PFTs: 30 min, 1, 2 and 3h post-dose |
| 12. | Visits 3 and 4**: 
 • Pre-dose PFT: 10 minutes prior to dosing • Post-dose PFTs: 30 min, 1, 2, 3, 4, 6, 8, 10, 11h50' • Inhalation of evening dose of study medication (12:00) • Post evening dose PFTs: 12h30', 13, 14, 22, 23h and 24h |
| 13. | Dispense rescue medication as needed. |
| 14. | The preferred sequence of procedures is as follows: 
 1. CAT (where applicable) 2. SGRQ (where applicable) 3. Physical Exam (where applicable) 4. 12-lead ECG (where applicable) 5. Labs (where applicable) 6. Pulmonary Function Test (pre-dose) |
| 15. | ECG: 12-lead ECG recording at screening (Visit 1) for inclusion in the study. |
| 16. | Patients on treatment with a LAMA at study entry will receive open label Atrovent HFA during the run-in period, per Investigator's discretion. This medication must be collected at Visit 2. |
| 17. | Medication use: From dose counter on Respimat [®] and Diskus [®] devices. |
| 18. | The 4-week screening period (between Visit 1 and Visit 2) may be extended by up to 4 weeks for administrative reasons and/or to meet wash-out requirements. (see Section 6.1). |

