Pulmonary function testing (PFT) will be conducted at the screening visit (Visit 1) to determine patient eligibility.

Analysis of clinical laboratory samples will be performed by a Central Lab. Any abnormal laboratory finding at Visit 2, which is considered by the investigator to be clinically relevant, will be recorded as baseline condition.

Adverse events will be documented throughout the trial, i.e. starting with informed consent and ending 21 days after administration of the last dose of trial medication. Further details of the assessments conducted throughout the study period are provided in the [Flow Chart](#) and [Section 6](#).

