3.3.2 Inclusion criteria

1. All patients must sign an informed consent consistent with FDA regulations prior to participation in the trial, which includes medication washout and restrictions.
2. All patients must have a diagnosis of chronic obstructive pulmonary disease [[P11-05865](#)] and must meet the following spirometric criteria:

Patients with a post-bronchodilator $30\% \leq FEV_1 < 80\%$ of predicted normal (ECSC, [[R94-1408](#)]); and a post-bronchodilator $FEV_1/FVC < 70\%$ at Visit 1 (see [Appendix 10.5](#) for ECSC predicted normal equations)

3. Male or female patients, 40 years of age or older.
4. Patients must be current or ex-smokers with a smoking history of more than 10 pack years. (see [Appendix 10.5](#) for calculation): Patients who have never smoked cigarettes must be excluded.
5. Patients must be able to perform, according to investigator's judgment, all trial related procedures including:
 - Technically acceptable pulmonary function tests (spirometry)
 - Completion of study questionnaires
6. Patients must be able to inhale medication in a competent manner (in the opinion of the investigator) from the Respimat[®] and Diskus[®] inhalers ([Appendix 10.1](#) and [10.2](#)) and from a metered dose inhaler (MDI).

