6.2.1 Screening and run-in period(s)

To keep the number of screen failures and patients with avoidable washout procedures as low as possible, patients should be very carefully selected for this trial. Therefore, investigators should make a preliminary check of major inclusion and exclusion criteria when considering patients for enrolment in the trial.

Patient numbers will be assigned in the IRT system and transferred from there to/into EDC, thereby creating the subject in EDC.

Details of any patient who is screened for the trial but is found to be ineligible must be entered in the Enrolment log and documented in the eCRF.

Eligibility will be assessed at Visits 0 and 1 and confirmed at the randomization visit (Visit 2).

Run-in Period

- Informed Consent will be obtained at Visit 0, prior to patient participation in the trial, which includes any medication washout procedures or restrictions. Upon obtaining Informed Consent, the patient will be instructed on the medication washout and other restrictions needed for the screening pulmonary function test at Visit 1.
- The patient will receive instructions on the as needed use of the albuterol MDI (as rescue medication) that will be dispensed at this visit.
- In case the patient has to wash-out of a LAMA in the run-in, at the discretion of the investigator, Atrovent HFA will be dispensed at this visit.
- A preliminary check of inclusion/exclusion criteria is recommended at Visit 0 to avoid unnecessary washout procedures in non-eligible patients.

- Any adverse events and concomitant therapies will be recorded
- The patient will receive a trial identification card.

Observations and procedures at Visit 1

Refer to the [Flow Chart](#) for procedures to be conducted at this visit:

- Demographics/Baseline conditions, Physical, COPD characteristics, lab testing, pregnancy testing, ECG, review of smoking status and concomitant medications and AE check.
- Pulmonary function testing with the MasterScope® CT spirometer will be conducted between 7:00 and 10:00 a.m. immediately prior to (-10 min) and ≥10 minutes and up to 45 minutes after the inhalation of 4 puffs of salbutamol (albuterol), (reversibility testing).
- Patients qualified to enter the 4-week (up to 12-week) screening period of the trial will be issued additional rescue medication if needed.
- Patients will receive training and instructions on:
 - the use of the Respimat® Inhaler using the training Respimat® Inhaler containing placebo

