10.5 ADDITIONAL INFORMATION REGARDING IN/EX CRITERIA

Reversibility testing (P05-12782)

At the screening visit (Visit 1), following the completion of three acceptable pre-bronchodilator forced expiratory manoeuvres, albuterol will be administered to each patient in order to document the degree of reversibility. Immediately after (within 10 min) pre-bronchodilator forced expiratory manoeuvres and after a gentle and incomplete expiration, a dose of 100 µg of salbutamol (albuterol) is inhaled in one breath to total lung capacity (TLC). The breath is then held for 5–10 s before the subject exhales. Four separate doses (total dose 400 µg) are delivered at approximately 30-s intervals (this dose ensures that the response is high on the salbutamol dose–response curve). Three additional, acceptable post-bronchodilator forced expiratory manoeuvre tests are recorded ≥10 minutes and up to 45 minutes later after the last dose of albuterol is inhaled.

Calculation of predicted normal values according to ECSC (R94-1408)

For height measured in inches

Males: FEV_1 predicted (L) = 4.30 x [height (inches)/39.37] - 0.029 x [age (yrs)] - 2.49

Females: FEV_1 predicted (L) = 3.95 x [height (inches)/39.37] - 0.025 x [age (yrs)] - 2.60

For height measured in meters

Males: FEV_1 predicted (L) = 4.30 x [height (m)] - 0.029 x [age (yrs)] - 2.49

Females: FEV_1 predicted (L) = 3.95 x [height (m)] - 0.025 x [age (yrs)] - 2.60

Calculation of number of pack years

$$\text{Pack years} = \frac{\text{Number of cigarettes/day}}{20} \times \text{years of smoking}$$

Boehringer Ingelheim

BI Trial No.: 1237-0063

c13020187-03

06 March 2018

Trial Protocol

Page 94 of 125

Proprietary confidential information © 2018 Boehringer Ingelheim International GmbH or one or more of its affiliated companies

Boehringer Ingelheim

BI Trial No.: 1237-0063

c13020187-03

06 March 2018

Trial Protocol

Page 95 of 125

Proprietary confidential information © 2018 Boehringer Ingelheim International GmbH or one or more of its affiliated companies

Boehringer Ingelheim

BI Trial No.: 1237-0063

c13020187-03

06 March 2018

Trial Protocol

Page 96 of 125

Proprietary confidential information © 2018 Boehringer Ingelheim International GmbH or one or more of its affiliated companies

Boehringer Ingelheim

BI Trial No.: 1237-0063

c13020187-03

06 March 2018

Trial Protocol

Page 97 of 125

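### Does the sentence in Protocol 5.2.1 that places eligibility and reversibility spirometry at Visit 2 put the baseline FEV1 at risk?

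*Protocol*

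**What the plan says.** Protocol 5.2.1, the section on lung function testing, states: "At Visit 2, pulmonary function tests will be performed to determine patient eligibility and assess bronchial reversibility (for patient characterization". It then refers the reader to Appendix 10.5 for how reversibility is tested, and to the Flow Chart for the timing of the tests.

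Two places put eligibility spirometry at Visit 1:

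- Section 3.1: "Pulmonary function testing (PFT) will be conducted at the screening visit (Visit 1) to determine patient eligibility".
- Section 3.3.2, inclusion criterion 2, which sets the post-bronchodilator thresholds "at Visit 1 (see [Appendix 10.5](#) for ECSC predicted normal equations").

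Three places put reversibility testing at Visit 1:

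- Flow Chart note 10: "Visit 1: Reversibility testing using 400µg albuterol".
- Section 6.2.1, in the list of Visit 1 procedures, which has spirometry before and "after the inhalation of 4 puffs of salbutamol (albuterol), (reversibility testing").
- Appendix 10.5: "At the screening visit (Visit 1), following the completion of three acceptable pre-bronchodilator forced expiratory manoeuvres, albuterol will be administered".

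Flow Chart note 11 gives the Visit 2 schedule as "Two pre-dose PFTs: One at 1hour pre-dose and a second at 10 minutes prior to inhalation of dose of trial medication", followed by tests at 30 minutes, 1, 2 and 3 hours after dosing. It lists no albuterol. Section 5.1.1 takes baseline FEV1 from that visit, ahead of the first randomised dose: "The mean of the two pre-dose pulmonary function test measurements at Visit 2, 1 hour prior and 10 minutes prior to the administration".

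**The concern.** The section that governs the primary measurement names a different visit from the rest of the protocol, and that visit is the one that supplies baseline. Baseline FEV1 is subtracted to form the primary endpoint and is also a covariate in the primary model. If a site took 5.2.1 literally and gave albuterol on the morning of Visit 2, one or both baseline readings could be raised and the change from baseline lowered. If some sites did this and others did not, baseline would also be noisier.

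Such a test could be judged to breach the 8-hour washout of short-acting beta-agonists in Protocol 4.2.2.1, and so be listed as important violation D1 in SAP Table 6.2: 1. That would put patients at risk of exclusion from the per-protocol set.

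**Working it through.** There is no plan figure to reproduce. The check has four steps.

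**1. Count the statements.**

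| Place | Subject | Visit named |
|---|---|---|
| 5.2.1 | eligibility and reversibility | 2 |
| 3.1 | eligibility | 1 |
| 3.3.2, criterion 2 | eligibility | 1 |
| Flow Chart note 10 | reversibility | 1 |
| 6.2.1 | reversibility | 1 |
| Appendix 10.5 | reversibility | 1 |

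One place names Visit 2 and 2 + 3 = 5 name Visit 1. Each of the five covers one half of the 5.2.1 sentence, and together they cover both. Section 6.2.1 also says that eligibility is confirmed at Visit 2. That is a re-check of criteria and does not explain a reversibility test there.

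**2. See where the sentence leads.** A reader of 5.2.1 who wants to carry out the test must go to Appendix 10.5, which names Visit 1. A reader who wants the timing must go to the Flow Chart, which puts the test in note 10 (Visit 1) and omits it from note 11 (Visit 2). By Visit 2 the thresholds of criterion 2 have already been applied, since 6.2.1 admits to the screening period only patients who qualified at Visit 1. No rule says what a second result would decide.

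**3. Suppose a site did it anyway.** Section 4.1.4.1 sets first dosing at 07:00 to 10:00. The first baseline test, one hour earlier, falls at 06:00 to 09:00, and the second, ten minutes before dosing, at 06:50 to 09:50. The first governs the washout: 06:00 and 09:00 minus 8 hours gives 22:00 and 01:00. Albuterol given that morning before a baseline test therefore falls inside the 8 hours. Section 5.2.1 gives no order, so the effect depends on when albuterol is given. Let it raise FEV1 by *d*:

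- Before both pre-dose tests: baseline rises by (*d* + *d*)/2 = *d*.
- Between them: baseline rises by (0 + *d*)/2 = *d*/2.
- After both: baseline does not change. Only the Visit 2 post-dose tests could be affected, and these enter neither the primary nor the secondary week-12 endpoints (5.1.1, 5.1.2).

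The two lines with a rise treat *d* as equal at both readings, for illustration.

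**4. Carry it to the treatment contrast.** Let a share *p* of patients have baseline raised by *d*. The test precedes the first dose and assignment is random and blinded, so *p* and *d* have the same expectation in both arms. Each arm's mean change falls by *p* × *d*, and the difference moves by (−*pd*) − (−*pd*) = 0. The primary model also includes baseline and baseline by visit. With those terms present, modelling the change or the raw week-12 value gives the same treatment contrast, so a disturbed baseline acts only through the covariate. It could cost some precision but does not shift the contrast systematically.

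**The case for a change.** The strongest case for acting is that the sentence can be carried out as written. The two pre-dose tests are 60 − 10 = 50 minutes apart. Appendix 10.5 allows the post-albuterol test from 10 to 45 minutes after the last puff, so at nominal times a reversibility test could be fitted between them. Note 11 also prints an asterisk beside Visit 2, and the single-asterisk footnote points to the reversibility instructions, so the Flow Chart is not perfectly clean.

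Nor does the analysis plan provide for this case. The primary analysis uses the full analysis set. The rescue-medication rules (Protocol 7.5; SAP 6.6.1 for Visits 3 and 4) do not speak of a scheduled test. An affected baseline could therefore stay in the primary analysis, and the correction would cost one sentence.

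The textual conflict stands, and so does the need to check the asterisk. The lung function row of the Flow Chart carries the same mark, so it may be a stray.

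The consequences are weaker. A site would have to follow one sentence against the Flow Chart, the Visit 1 procedure list, the inclusion criterion and the appendix that the sentence relies on. Whether a test done on the protocol's own instruction counts as improper washout is not stated; D1 is decided at the blinded report planning meeting. Exclusion under D1 would touch only the per-protocol set, whose analysis is supportive and is run only if that set is below 90% of the full analysis set.

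**Conclusion.** The inconsistency is genuine and is best read as a clerical slip. The statements on which visit carries eligibility and reversibility spirometry, and the asterisk in note 11, must be reconciled by the sponsor so that one visit is named throughout. That is editing. It alters neither the schedule that the Flow Chart already sets out, nor the baseline definition, nor the analysis, so nothing in the statistical plan needs to change.

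The expected effect on the treatment difference is zero. Any effect on within-arm change or on precision cannot be sized from the documents, and would arise only if a site gave albuterol before a Visit 2 pre-dose test. The conclusion rests on two assumptions: sites work from the Flow Chart and the appendix to which 5.2.1 refers them, and any departure occurs before the first dose and without knowledge of treatment. The second follows from the double-blind design. The first is a judgement, well supported by the cross-references.
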